- To examine the associations of SPM approaches using all available normalized F-FDG-PET SUVR data and volumetric MRI data with the following clinical measures:
  - ADAS-cog13
  - ADCS-ADL23
  - Composite Scales (selected)
- Comparisons of measures of brain MRI hyperintensities by treatment group; subgroup analyses by previous treatment status of AChEIs and/memantine (prior use or never used) will also be performed, including for the combined LMTM 8-mg/day and placebo groups
- Population pharmacokinetics (to be subject to a section in the SAP or a separate SAP and report)
- To evaluate the influence of *ApoE* genotype (in subjects who provide legally acceptable consent) on the primary and selected secondary endpoints

A number of exploratory comparisons with external data may also be performed, to be specified in the SAP. These include comparisons of LMTM 16 mg/day or LMTM 8 mg/day on the following:

- Comparison of annualized rates of atrophy in a range of brain regions (including temporal lobe and whole brain) with the estimated decline for subjects with MCI-AD and mild AD with MMSE in the range of 20-27 not receiving either of the standard

treatments for AD (AChEIs and/or memantine) from the ADNI; this will be repeated for the entire MMSE range used in this study

- To compare the primary and selected secondary imaging and efficacy endpoints at 52 weeks with pooled mild AD subjects in control groups (subjects receiving LMTM at any dose in combination with an AChEI and/or memantine) from the LMTM Phase 3 trials (Studies TRx-237-005 and TRx-237-015) with baseline MMSE in the range of 20-26; this will be repeated for the entire MMSE range used in this study
- Comparison of decline in temporal lobe F-FDG-PET SUVR with the estimated decline for subjects with mild AD (CDR 0.5 at Screening) not receiving either of the standard treatments for AD (AChEIs and/or memantine) from the ADNI
- Accounting for and using historic data more generally such as placebo decline or treatment effects as priors to inform the analyses of this study.

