### Other Tests

Serum Pregnancy test  
Vitamin B12 / Folate  
Haptoglobin  
Thyroid Stimulating Hormone (TSH)  
Glucose-6-Phosphate Dehydrogenase (G6PD)  
*ApoE* (in subjects who consent for this)  
Blood sample for MT concentration

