Two open-label, delayed-start phase objectives have been added: determination if there is a difference in disease progression on the co-primary clinical endpoints and MRI imaging endpoint for subjects who started treatment in the double-blind phase and those who started in the open-label, delayed-start phase ( i.e. , “early” and “late” LMTM starters, respectively), and assessment of safety and tolerability of LMTM given for up to 104 weeks. Additional statistical analysis for the open-label phase has been defined.	Section 9.2.2 Open-Label, Delayed-Start Phase Section 17 Statistical Analysis Section 17.1.3 Secondary Endpoint for Open-Label, Delayed-Start Phase
Sample size estimations and study power to determine treatment effect have been revised based upon changes to primary treatment group, study population, co-primary clinical endpoints, and length of the double-blind treatment period of the study. Sample size estimations have also been	Section 17.2 Number of Subjects and Sample Size Calculation

Summary of Changes	Affected Sections in Revised Protocol (Version 5.0)
added for the open-label, delayed-start treatment period of the study.	
Clarification is provided that the primary efficacy analyses for FDA will be based on the E-MITT, MI-MITT, or I-MITT population (depending on endpoint), and for EMA on the ITT population. The co-primary efficacy endpoints and MRI will be analyzed using a linear mixed model for repeated measures with unstructured covariance matrix, and  F-FDG-PET analyzed using an ANCOVA, with covariates for this model adjusted accordingly.	Section 17 Statistical Analysis Section 17.4 Clinical Efficacy and Imaging Analysis Section 17.4.2 FDA Analysis
Evaluation of the influence of ApoE genotype (in subjects who provide legally acceptable consent) on the primary and selected secondary endpoints is now an exploratory endpoint (previously a secondary endpoint).	Section 9.2 Secondary Objectives Section 17.1.2 Secondary Efficacy Endpoints for Double-Blind Treatment Period Section 17.5 Exploratory Analyses

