## 5.9. Efficacy Evaluation

The primary objective of the final amended version of the study protocol (see Section 1.1) is to evaluate the efficacy of HMTM 16 mg/day compared with control over 52 weeks in patients with AD using the MMRM (including the nominal visits Week 13, Week 26, Week 39 and Week 52), including the randomization stratification variables (see Section 2.6) as fixed factors, the respective efficacy Baseline value as covariate, and the treatment indicator (plus its interaction term with the visit variable). The co-primary endpoints are the difference between HMTM 16 mg/day and control in ADAS-cog11 and ADCS-ADL23 at Week 52.

The next section will give the definitions of the estimands, which are then used in the following efficacy endpoint analysis sections. As a reminder to Section 5.2 the pre-defined analysis sequence is MITTv5 analysis followed by the estimands analysis based on ITTv5. Despite the definition of this sequence, the MITT based analysis is primary for the FDA while the ITT based analysis is considered primary for the EMA.

Regarding the MITT analyses, in subjects who have initiated treatment with an AChEI and/or memantine, assessments made after initiation of such treatment are not considered valid as they could confound the interpretation of the results and will be excluded. Such subjects and affected assessments will be identified prior to unblinding. Sensitivity analyses will be provided for the primary and selected secondary analyses including all data (MRI whole brain volume, and F-FDG-PET temporal lobe).

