### 5.9.2. Primary Efficacy Endpoint Analysis

#### 5.9.2.1. MITT Population Analysis

Data will be analyzed based on the E-MITTv5 population (see Section 3.1.1) using a restricted maximum likelihood-based (REML) MMRM, including a nominal visit variable, the treatment indicator and the interaction term between treatment and visit, the randomization stratification variables (see Section 2.6) as fixed factors, and the respective efficacy Baseline value as covariate; with an unstructured covariance matrix and the Kenward and Roger method of calculating the denominator degrees of freedom for the tests of fixed effects.

Sample SAS code (will be fully validated at the analysis stage):

```

PROC MIXED DATA=dataset METHOD=REML COVTEST;
  CLASS subject treatment(REF='Control') visit severity(REF='moderate') region(REF='Europe')
  prioruse(REF='None');
  MODEL scorediff = treatment/visit severity region prioruse scorebl / SOLUTION CL
  DDFM=KENWARDROGER;
  REPEATED visit / SUB=subject TYPE=UN;
  LSMEANS treatment*visit visit / CL;
  *BY_IMPUTATION_;
  LSMESTIMATE treatment*visit "intervention effect at Week 52" 0 0 0 1 0 0 0 -1 / CL;
  *Summary statistics for treatment difference based on LSM
  LSMESTIMATE treatment*visit "intervention effect at Week 13" 1 0 0 0 -1 0 0 0 / CL;
  LSMESTIMATE treatment*visit "intervention effect at Week 26" 0 1 0 0 0 -1 0 0 / CL;

```

Sponsor:	TauRx Therapeutics Ltd.		
Protocol:	TRx-237-039		
Document Version No.:	3.0	Document Date:	07-JUN-2023

*LSMESTIMATE treatment\*visit "intervention effect at Week 39" 0 0 1 0 0 0 -1 0 / CL;  
RUN;*

If the mixed model does not converge, the unstructured covariance matrix is replaced by firstly, an auto-regressive covariance structure then by a compound symmetry covariance structure. If the model still does not converge, the randomization stratification variables will be removed, in the following order: region, prior AChEI and/or memantine use, MMSE.

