#### **Supplementary and other sensitivity analyses**

Supplementary analyses are (starting population: E-MITTv5):

- Including subjects randomized before study protocol version 5.0 (E-MITT population)
- Restricted to the PP population
- Restricted to the completers (subjects who did not stop the study or the study medication early, during the double-blind treatment phase)
- Include assessments after initiation of an AChEI and/or memantine, if more than 5% of the randomized subjects initiated AChEI and/or memantine during the double-blind treatment phase
- Restricted to all visits not potentially confounded by intercurrent illnesses, COVID-19, and concomitant medications (which includes assessments after initiation of an AChEI and/or memantine) as identified during the BDRM
- Stratified by subgroups. If the subgroup consists of less than 10% of the randomized subjects, only summary statistics will be presented.
  - o AChEI/memantine use (prior use, never used) [binary]
  - o Verified AD diagnosis (probable AD, MCI-AD) [binary]
  - o MMSE (16-19, 20-25, and 26-27), in case of mis-stratification the actual value is used

Sponsor:	TauRx Therapeutics Ltd.		
Protocol:	TRx-237-039		
Document Version No.:	3.0	Document Date:	07-JUN-2023

- MMSE (16-21, 22-27)
- CDR (0.5, 1 or 2) [binary], in case of mis-stratification the actual value is used
- Age group (<75 years, ≥75 years) [binary]
- Sex (male, female) [binary]
- Race (White, non-White) [binary], Race = White (if checked as only race), otherwise Race = non-White (even if multiple races, including White, were checked)
- Geographic region (North America, Europe) [binary]
- Including the *ApoE* genotype as fixed factor (Presence of the ε4 Allele, Absence of the ε4 Allele) [binary]
- Both HMTM treatment groups pooled versus control

Sensitivity analyses are:

- If more than 5% of the randomized subjects have been mis-stratified, then the primary analyses will be repeated using the actual status at randomization
- Multiple imputation analysis (see Section 4.5.2)

For the two co-primary endpoints and their change from Baseline to Week 52, the empirical distribution functions for HMTM 16 mg/day and control will be compared graphically and using a Kolmogorov-Smirnov test. If the Week 52 visit value is not available, the last available on-treatment value will be used.

Sample SAS code (will be fully validated at the analysis stage):

```
PROC NPAR1WAY DATA=dataset EDF PLOTS=EDFPLOT;

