#### **5.10.8. *ApoE* Genotype**

A subject data listing will be provided for *ApoE* genotype data, including only the subjects who consented to this determination. In this listing, the genotype classification (presence/absence of the ε4 allele) will be given, but not the detailed genotype.

The influence of the genotype (presence/absence of ε4 allele) will be evaluated for the two co-primary endpoints and selected secondary endpoints (MRI whole brain volume, and F-FDG-PET temporal lobe) by adding the genotype classification as a fixed factor into the MMRM and ANCOVA model (see Section 5.9.2.1).

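### The ApoE analysis adds genotype to the four-visit MMRM as a lone main effect, so it yields no genotype estimate at Week 52 and understates a difference that grows over time

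*Protocol*

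**What the plan says.** The live objective is in Protocol 17.5, among the exploratory analyses: the influence of ApoE "genotype (in subjects who provide legally acceptable consent) on the primary and selected secondary endpoints". Section 28.4.6, the summary of changes for Version 5.0, words it as "Evaluation of the influence of ApoE genotype (in subjects who provide legally acceptable consent) on the primary and selected secondary endpoints" and records its move from secondary to exploratory status. Genotyping is optional, done only "in subjects who consent for this" (Protocol 28.2).

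SAP 5.10.8 names four endpoints (the two co-primaries, MRI whole brain volume and FDG-PET temporal lobe) and evaluates the influence of e4 status "by adding the genotype classification as a fixed factor into the MMRM and ANCOVA model". The supplementary list in SAP 5.9.2.1 has a matching bullet: "genotype as fixed factor (Presence of the ε4 Allele, Absence of the ε4 Allele) [binary".

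The MMRM is defined in SAP 5.9.2.1 as "including a nominal visit variable, the treatment indicator and the interaction term between treatment and visit, the randomization stratification variables", plus the baseline value, with an unstructured covariance. It runs over four visits, "including the nominal visits Week 13, Week 26, Week 39 and Week 52" (SAP 5.9). If it does not converge, an auto-regressive and then a compound symmetry structure replaces the unstructured one. Protocol 17.4.1 and SAP 5.1 place the co-primary endpoints at Week 52. FDG-PET uses an ANCOVA on a single post-baseline value (SAP 5.9.3.2).

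**The concern.** In this model treatment has its own effect at each visit and genotype does not. The fitted carrier versus non-carrier difference at Week 13 is forced to equal the one at Week 52. The question concerns Week 52 changes, and no Week 52 genotype estimate comes out of the planned analysis.

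Change from baseline is zero at baseline by construction. If genotype acts on the rate of decline, the difference between carriers and non-carriers widens over the year, and a common offset is then an average over visits. The averaging is not even. Generalised least squares gives more weight to visits with smaller variance, and those are usually the early ones, where the genotype difference is smallest. The report could show a small genotype difference and be read as little influence when the Week 52 difference is material.

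The SAP uses comparable terms elsewhere. It has a baseline-by-visit sensitivity model (5.9.2.1) and MRI-baseline-by-treatment interactions for both co-primaries (5.10.5).

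**Working it through.** **Inputs from the documents.** Four visits; unstructured covariance; genotype as a main effect only; ADAS-cog11 Week 52 SD 5.9 (SAP 5.3).

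**Assumed, because the documents do not give them.** The shape of the genotype difference over time, the SDs before Week 52 and the between-visit correlations.

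**The plan's own figures.** There is no ApoE effect size or power to reproduce. The SDs can be checked against the stated power. With 25% withdrawal, n = 200 × 0.75 = 150 per arm.

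- ADAS-cog11: SE = 5.9 × √(2/150) = 0.681; 2.6/0.681 = 3.82; 3.82 − 1.96 = 1.86, so power is 96.8% (96.7% by noncentral t; SAP 96.7%).
- ADCS-ADL23: SE = 8.5 × √(2/150) = 0.981; 3.4/0.981 = 3.46; 3.46 − 1.96 = 1.50, so power is 93.4% (93.2% by noncentral t; SAP 93.2%).

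Both reproduce, so 5.9 is a sound Week 52 SD to work from.

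**Formula.** Let the true difference at the four visits be Δ × g, with g = (0.25, 0.50, 0.75, 1.00) for linear growth to Δ at Week 52. A constant effect fitted with covariance V has expectation Δ × (1′V⁻¹g)/(1′V⁻¹1). The weights are w = V⁻¹1/(1′V⁻¹1), and recovery is the weighted sum of g.

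**Constant variance.** Under compound symmetry all weights are 0.25, so recovery is (0.25 + 0.50 + 0.75 + 1.00)/4 = 0.625. An AR structure gives symmetric weights and the same 0.625 at any correlation. The homogeneous forms of the two fallback structures also give this figure.

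**Rising variance, one case in full.** SDs 3.54, 4.33, 5.11 and 5.90 (Week 13 SD = 0.6 of Week 52), compound symmetry 0.6. Weights are 0.766, 0.285, 0.041 and −0.092. Recovery = 0.766 × 0.25 + 0.285 × 0.50 + 0.041 × 0.75 − 0.092 = 0.27. Week 13 dominates, and Week 52 gets a slightly negative weight.

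**Grid of recovery fractions** (SD linear in week):

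| Week 13 SD / Week 52 SD | CS 0.3 | CS 0.6 | AR 0.3 | AR 0.6 |
|---|---|---|---|---|
| 1.0 | 0.625 | 0.625 | 0.625 | 0.625 |
| 0.9 | 0.58 | 0.54 | 0.60 | 0.58 |
| 0.8 | 0.54 | 0.45 | 0.57 | 0.53 |
| 0.6 | 0.44 | 0.27 | 0.49 | 0.43 |

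A random-slope-plus-error model, baseline-adjusted and scaled to SD 5.9 at Week 52, gives 0.19 to 0.57. Independent increments give 0.25. At the extreme, compound symmetry of 0.8-0.9 with a ratio of 0.6 gives about 0.01 to −0.27.

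**Simulation with an unstructured fit.** The lone main effect recovered 27% (ratio 0.6, CS 0.6), 37% (0.6, AR 0.7), 44% (0.75, CS 0.5) and 60-62% (constant SD). A genotype-by-visit model read at Week 52 recovered 96-100% in the same scenarios.

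**Illustration in units.** Assume a 2.0-point Week 52 difference and 300 genotyped subjects with complete data, split 180/120. The Week 52 contrast has SE = 5.9 × √(1/180 + 1/120) = 0.695 and power 82%. With ratio 0.6 and CS 0.6, the main effect is expected to return 2.0 × 0.273 = 0.55 points with SE 0.40, power about 28%. With ratio 0.6 and AR 0.3 it returns 2.0 × 0.491 = 0.98 points with SE 0.32, power about 86%. The size is understated in both cases. Power falls in the first and not in the second.

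**The case against.** **The analysis is exploratory.** No alpha, gatekeeping or primary inference depends on it, and Protocol 17.5 introduces its list as possible analyses. This stands and sets the severity.

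**A main effect can be right for another purpose.** The SAP 5.9.2.1 bullet sits among supplementary analyses of the treatment effect. Read as covariate adjustment of the treatment contrast, a genotype main effect is ordinary practice, just as the strata enter as main effects. That stands for the treatment contrast. It does not answer SAP 5.10.8, which says that the influence of genotype itself is evaluated this way.

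**The difference may not grow.** If it were complete by Week 13 and then flat, the main effect would recover all of it. This is possible, and the documents do not settle it. A genotype-by-visit term would show which pattern holds; the planned model assumes one.

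**The percentages are not the plan's.** This stands. A reader might take a narrow range such as 27-49% as a property of the SAP, but it belongs to particular assumed SDs and correlations. Nor is loss of power assured, as the illustration shows.

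**Further inferences that the documents do not support.** A reader might conclude that the plan is defective because it cannot show whether genotype modifies the drug effect, or because subjects without a genotype leave the model. Protocol 17.5 asks about the influence of genotype on the endpoints, in consenting subjects only. Effect modification is not a stated aim, and the restricted set is by design.

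**Conclusion.** The point holds as a minor one. For ADAS-cog11, ADCS-ADL23 and MRI whole brain volume, the planned model imposes a common genotype difference at Weeks 13 to 52 and gives no estimate at Week 52. That follows from the model as written and needs no assumption.

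The size does need assumptions. With linear growth of the difference, recovery is about 62% under constant variance and roughly 20-60% under variance that rises over visits. It is lower still if correlations are very high and equal, and it approaches 100% if the difference appears early and plateaus.

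Two stronger readings fail. FDG-PET does not share the problem, because its ANCOVA has one post-baseline value. The primary treatment test is also untouched: its model contains no genotype term.

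**What to change.** In SAP 5.10.8 and the matching bullet in 5.9.2.1, add genotype-by-visit alongside the genotype main effect in the MMRM, and report the carrier minus non-carrier contrast at Week 52 with its 95% confidence interval. The FDG-PET ANCOVA needs no change on this account.

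As optional exploratory additions, fit treatment-by-genotype and treatment-by-genotype-by-visit and report the 16 mg minus control difference at Week 52 by carrier status. Refit the primary model on the genotyped subset, so that any shift in the treatment contrast can be attributed to the covariate or to the subject set.

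SAP section 10 states that version 3.0 followed the 28-APR-2022 data snapshot and partial unblinding for the double-blind analysis. Terms added now should be labelled post hoc.

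No new data are needed. With two genotype levels and four visits, the genotype-by-visit term adds three parameters. The genotype interval is wider, because the Week 52 contrast no longer averages over the earlier visits: in the two cases above the SE is 0.695, against 0.32 to 0.40.

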**28.4.7 Protocol Version 5.1**

The protocol for Study TRx-237-039 (Version 5.0 dated 9 July 2019) has been revised primarily to include modifications to the exclusion criterion regarding hematological abnormalities (reverting to the original criterion), clarifications to background information for the study drug and the efficacy objectives/statistical analyses, as well as updates to responsible personnel. A summary of the key changes and affected sections is provided below.

Additional revisions are editorial and are intended to correct typographical errors or add further clarification.

Summary of Changes	Affected Sections in Revised Protocol (Version 5.1)
Responsible Personnel	
Charles River Laboratories Edinburgh Ltd has been added to responsible personnel for analysis of MT concentrations (cross-validation purposes only).	Section 4 Responsible Personnel
Subject Enrollment and Withdrawal	
The provision for discussion of potentially exclusionary low screening Hgb values with the Medical Monitor has been removed; Hgb values below age/sex appropriate lower limit of the central laboratory normal range are once again exclusionary regardless of etiology.	Synopsis Section 11.2 Exclusion Criterion #12 Section 11.3 Re-screening
Study Drug	
Clarification has been added that the increased incidences of pancreatic islet cell adenoma and adenoma or carcinoma (combined) in male rats, reported in a 2-year carcinogenicity study performed by the National Toxicology Program, were attributed to MTC by FDA (as interpreted by the FDA Executive Carcinogenicity Assessment Committee).	Section 8.1.2 Nonclinical Data
Clarification has been added that the magnitude of concentration-dependent treatment effects was reduced when LMTM was given to subjects who were concurrently using (rather than prior use of) AChEIs and/or memantine.	Section 8.1.3.3 Efficacy
Objectives and Endpoints / Statistical Analyses	
To correct a typographical error in the synopsis regarding the first secondary endpoint (the comparison of the LMTM dose of 16 mg/day with the placebo group in annualized rate of whole brain atrophy, rather than temporal and parietal lobe atrophy).	Synopsis
To clarify the exploratory analysis for comparison of decline in temporal lobe  F-FDG-PET SUVR with the estimated decline for subjects with mild AD (CDR 0.5); reference to the MMSE range has been removed. The analyses will be further described and clarified in the SAP.	Section 17.5 Exploratory Analyses

### 28.4.8 *Protocol Version 6.0*

The protocol for Study TRx-237-039 (Version 5.1 dated 05 February 2020) has been revised to incorporate modifications to the study conduct and monitoring, guidance for continued data collection and analysis, and ongoing risk assessment due to the COVID-19 Public Health Emergency. In addition, the total number of subjects to be randomized has increased, and updates have been incorporated for contact information for responsible personnel, as well as modifications and/or clarifications to investigator responsibilities, study assessments, and statistical analyses. Reference to a separate plan has been included for additional analyses to be undertaken of the blinded F-FDG-PET and MRI data for scientific research and quality control purposes. A summary of the key changes and affected sections is provided below.

Additional revisions are editorial and are intended to correct typographical errors and editorial inconsistencies as well as to add clarification.

Summary of Changes	Affected Sections in Revised Protocol (Version 6.0)
Changes due to COVID-19 Public Health Emergency	
The post-Baseline visits for safety, PK, and genotyping blood sample collection as well as efficacy assessments may be completed in-clinic at the site, in the home, or at other safe, suitable alternative location if deemed necessary to protect subjects due to COVID-19. Acceptable procedures for safety and efficacy assessments, blood sample collection, shipment, and analysis are described. Study visit windows may be further extended at the discretion of the Sponsor when justification is provided.	Synopsis Section 10.1 General Description Section 10.2.1 Changes to Study Conduct Section 10.5.3 Assessments in the Open-Label, Delayed-Start Phase Section 13.7 Contraceptive Measures Section 15.4 Safety Assessments and Procedures Section 15.5.1 MT Concentration Section 16.7 Serious Adverse Event Reporting
Alternative arrangements for dispensing study drug supplies may be permitted if deemed necessary to protect subjects due to COVID-19. Requirements for obtaining subject consent consistent with local and national requirements, maintaining the specified study drug storage conditions, and handling, accountability, and compliance monitoring will be addressed and documented.	Synopsis Section 10.1 General Description Section 10.2.1 Changes to Study Conduct Section 12.2 Study Regimens Section 12.5 Dispensing
If a subject is undergoing screening assessments and cannot have assessments performed due to COVID-19, the subject should be put on screening pause until such times as COVID-19 impacts have ceased.	Synopsis Section 10.2.1 Changes to Study Conduct Section 10.5.1.1 Diagnostic and Cognitive Eligibility Assessments Section 11.3 Re-screening
The Sponsor may approve subject randomization without a brain  F-FDG-PET scan if the scan cannot be performed due to COVID-19.	Synopsis Section 10.1 General Description Section 10.2.1 Changes to Study Conduct Section 10.5.1 Screening Assessments Section 10.5.2 Baseline and Post-randomization Assessments in Double-Blind Treatment Period
All MRI scans are to be performed at approved MRI centers using approved scanners; no alternative scanners will be accepted; there is to be no change in scanner for a given subject over the course of the study. Guidance will be provided for scheduled MRI visits at approved imaging centers that may be closed due to COVID-19, including acceptable windows outside of the scheduled visit window during which MRI scans can still be performed and would be accepted for analysis.	Synopsis Section 10.1 General Description Section 10.2.1 Changes to Study Conduct Section 15.3.1 General Considerations Section 15.3.3.2 MRI
All  F-FDG-PET scans are to be performed at approved PET centers using approved scanners; there is to be no	Synopsis Section 10.1 General Description Section 10.2.1 Changes to Study Conduct

Summary of Changes	Affected Sections in Revised Protocol (Version 6.0)
change in scanner for a given subject over the course of the study.	Section 15.3.1 General Considerations
The ADAS-cog 13 may also be performed by videoconference and the MMSE, ADCS-ADL 23 , and CDR may be performed by speakerphone. The remote efficacy scale assessments are now described in the protocol.	Synopsis Section 10.1 General Description Section 10.2.1 Changes to Study Conduct Section 15.2.2 Instruments
Clarification is now provided that multiple study partners participating only as caregivers will be permitted for a given subject, either simultaneously or as replacements for previous study partners, with no specified maximum. A maximum total of two study partners participating as informants ( i.e. , one replacement) would normally be permitted for a given subject; however, up to a total of four study partners ( i.e. , three replacements) are permitted if circumstances change due to COVID-19. Information obtained from study partners participating as informants will be appropriately identified to distinguish each informant in the event that a given subject has more than one study partner providing data for analysis.	Synopsis Section 10.1 General Description Section 10.2.1 Changes to Study Conduct Section 10.5.1 Screening Assessments Section 10.5.1.1 Diagnostic and Cognitive Eligibility Assessments Section 11.4.2 Handling of Study Discontinuation / Withdrawal Section 11.4.3 Replacements Section 15.2.1 Raters
For PK blood sample collection at Visit 2, Visit 3, Visit 7, and Visit 10, the third sample to be collected approximately 4 hours after the dose is not required if the visit occurs in the home.	Synopsis Section 10.2.1 Changes to Study Conduct Section 10.5.2 Baseline and Post-randomization Assessments in Double-Blind Treatment Period Section 10.5.2.4 Other Assessments in Double-Blind Treatment Period Section 10.5.3 Assessments in the Open-Label, Delayed-Start Phase Section 10.5.3.4 Other Assessments in Open-Label, Delayed-Start Phase Section 15.5.1 MT Concentration
Sections have been added describing the Sponsor's ongoing risk assessment regarding the impact of COVID-19 on this study, including guidance for continued data collection and potential changes in site and remote monitoring procedures, as well as changes to statistical analyses.	Synopsis Section 10.2 Changes Implemented Due to COVID-19 Section 10.2.1 Changes to Study Conduct Section 10.2.2 Changes to Study Monitoring Section 10.2.3 Changes to Statistical Analyses Section 17.4.11 Sensitivity Analyses Section 17.9 Interim Analysis Section 18 Regulatory and Ethics Section 21.2 COVID-19 Risk Assessment ( new )
Responsible Personnel	
A DSSL 24-hour medical contact telephone number has been added for France.	Section 4 Responsible Personnel
Investigator responsibilities include supervising any individual or party to whom the investigator delegates trial-related duties and functions conducted at the trial site.	Section 18.4 Investigator Responsibilities
Study Population	
The number of randomized subjects has been increased: a sufficient number of subjects will be recruited such that approximately 500 subjects are enrolled; beginning with Version 5.0, approximately 450 subjects are to be enrolled and randomized in a 4:1:4 ratio (at the study level) to the LMTM 16-mg/day, LMTM 8-mg/day, and placebo groups. The inclusion criterion for an MMSE score of 16-27 (inclusive) at Screening will be subject to stratification requirements.	Synopsis Section 10.1 General Description Section 10.3 Study Population Section 11.1 Inclusion Criteria Section 12.2 Study Regimens Section 12.3 Randomization Section 17.2 Number of Subjects and Sample Size Calculation

Summary of Changes	Affected Sections in Revised Protocol (Version 6.0)
Imaging	
If subjects have an acceptable MRI scan or PET scan (the latter only in subjects who have a screening CDR of 0.5) already completed during the original Screening window, the scan does not require repetition.	Section 10.2.1 Changes to Study Conduct Section 10.5.1.1 Diagnostic and Cognitive Eligibility Assessments Section 11.3 Re-screening Section 15.3.3.1  F-FDG-PET
Reference is included to a separate plan and data transfer agreement that will capture standard procedures for additional exploratory analyses to be undertaken to characterize the blinded  F-FDG-PET and MRI data for scientific research and quality control purposes, which are separate from the study objectives.	Section 20.2 Imaging Data ( new )
Added consistent wording regarding baseline  F-FDG-PET scan in subjects who have a screening CDR of 0.5.	Synopsis Section 10.1 General Description Section 10.5.2.1 Imaging Efficacy Assessments in Double-Blind Treatment Period Section 11.3 Re-screening Section 13.1 AChEI and/or Memantine Section 15.3.3.1  F-FDG-PET
Safety	
Permanent discontinuation due to decreased creatinine clearance is only required in subjects if renal concerns arise.	Section 11.4.1 Handling of Subjects Who Discontinue Study Drug Section 16.11.2 Other Safety Reasons Requiring Discontinuation of Study Drug
Any abnormal laboratory test result from Screening assessments (prior to treatment) is to be added to the subject's medical history, unless deemed clinically significant by the medical assessor (MD/DO) in which case it will be recorded as an AE.	Section 15.4 Safety Assessments and Procedures Section 16.1 Definition of AEs, Period of Observation, and Recording of AEs
Other Assessments	
Guidance is now provided regarding collection of blood samples at early termination visits for determination of MT concentrations.	Synopsis Section 10.5.2 Baseline and Post-randomization Assessments in Double-Blind Treatment Period Section 10.5.2.4 Other Assessments in Double-Blind Treatment Period Section 10.5.3 Assessments in the Open-Label, Delayed-Start Phase Section 10.5.3.4 Other Assessments in Open-Label, Delayed-Start Phase Section 15.5.1 MT Concentration
Statistical Analyses	
The secondary efficacy endpoints to compare the difference in temporal lobe  F-FDG-PET change in SUVR normalized to pons in subjects with CDR 0.5 at Screening (LMTM 16 mg/day versus placebo, and LMTM 8 mg/day versus placebo) will now only be analyzed if a predefined threshold is reached for a sufficient number of subjects providing data as specified in the SAP.	Synopsis Section 9.2.1 Double-Blind Treatment Period Section 17.1.2 Secondary Efficacy Endpoints for Double-Blind Treatment Period

Summary of Changes	Affected Sections in Revised Protocol (Version 6.0)
Upon completion of the initial 52-week, double-blind, placebo-controlled treatment period, the database will be locked and unblinded for analysis, and an interim report will be prepared describing the complete efficacy and safety analyses of the double-blind phase; individual subject prior treatment assignment will not be divulged to subjects or individuals involved in the operational conduct of the ongoing open-label, treatment phase.	Section 10.1 General Description Section 10.7 Definition of End of Study Section 12.8 Breaking the Blind for Double-Blind Treatment Period Section 17.9 Interim Analysis
Due to the introduction of MTC spiking in the placebo arm with Protocol Version 5.0, the respective MITT populations will be restricted to subjects randomized to Protocol Versions 5.0 and above for the primary and key secondary analyses as per the SAP. The full MITT populations will be analyzed for these as a sensitivity analysis. Details will be provided in the SAP.	Section 17.3 Analysis Populations Section 17.4 Clinical Efficacy and Imaging Analysis
It is now indicated that the SAP will specify estimands to provide a more comprehensive assessment of the performance and efficacy of the drug accounting for various factors (importantly, drop-outs).	Section 17.4.4 Estimands
The last observation carried forward (LOCF) imputation has been removed from the statistical analyses.	Section 17.4.11.6 Last Observation Carried Forward (LOCF) Imputation (deleted)

